8.6 Statistical Methods

8.6.1 Statistical Methods for Efficacy Analyses

A summary of the primary analysis strategy for the primary and secondary efficacy endpoints is provided in [Table 10](#) below. The primary evaluation will be by central review for ORR, DCR, PFS, and DOR.

8.6.1.1 Objective Response Rate

The primary efficacy endpoint for this study is the ORR for each cohort, defined as the proportion of subjects who have response (CR or PR) prior to disease progression. In the rrPMBCL cohort, an exact binomial test will be conducted versus a fixed control rate. In both cohorts, the final analysis for the primary endpoint will be conducted when the last subject has reached the Week 12 response assessment or has discontinued study therapy.

The analysis will consist of the point estimate and 95% (90% for rrRS cohort) 2-sided exact CI using the Clopper-Pearson method which will have at least 95% (90% for rrRS cohort) coverage of the true rate.

Since an investigator may still continue to treat subjects with pembrolizumab who have progressed according to IWG criteria, exploratory analyses (point estimate and 90% 2-sided exact confidence interval) will be conducted for ORR to consider these subjects who later achieve PR or CR post-progression as responders. An additional exploratory analysis for ORR will be conducted based on the Lugano classification (Cheson, 2014 [2]).

8.6.1.2 Disease Control Rate

The DCR, defined as the proportion of subjects in the analysis population who have achieved a CR, PR or SD response prior to disease progression. The analysis will consist of the point estimate and 90% 2-sided exact CI; analogous to ORR, an exploratory analysis of DCR will be performed to consider subjects who continue to receive pembrolizumab and later achieve PR, CR or SD following initial progression.

8.6.1.3 Progression-Free Survival

The non-parametric Kaplan-Meier method will be used to estimate the PFS curve.

Since disease progression is assessed periodically, PD can occur any time in the time interval between the last assessment where PD was not documented and the assessment when PD is documented. For the primary analysis, for the subjects who have PD, the true date of disease progression will be approximated by the date of the first assessment at which PD is objectively documented per IWG criteria, regardless of discontinuation of study drug. Death is always considered as a confirmed PD event.

In order to evaluate the robustness of the PFS endpoint, we will perform two sensitivity analyses with a different set of censoring rules. The first sensitivity analysis is the same as the primary analysis except that it censors at the last disease assessment without PD when PD or death is documented after more than one missed disease assessment. The second sensitivity analysis is the same as the primary analysis except that it considers discontinuation of treatment or initiation of new anticancer treatment, whichever occurs later, to be a PD event for subjects without documented PD or death. The censoring rules for primary and sensitivity analyses are summarized in [Table 9](#).

Table 9 Censoring rules for Primary and Sensitivity Analyses of Progression-Free Survival

Situation	Primary Analysis	Sensitivity Analysis 1	Sensitivity Analysis 2
No progressive disease (PD) and no death; new anticancer treatment is not initiated	Censored at last disease assessment	Censored at last disease assessment	Censored at last disease assessment
No PD and no death; new anticancer treatment is initiated	Censored at last disease assessment before new anticancer treatment	Censored at last disease assessment before new anticancer treatment	Progressed at date of new anticancer treatment
PD or death documented after ≤ 1 missed disease assessment	Progressed at date of documented PD or death	Progressed at date of documented PD or death	Progressed at date of documented PD or death
PD or death documented after ≥ 2 missed disease assessments	Progressed at date of documented PD or death	Censored at last disease assessment prior to the ≥ 2 missed disease assessment	Progressed at date of documented PD or death
No PD and no death and lost to follow-up after ≥ 2 missed disease assessments	Censored at last disease assessment	Censored at last disease assessment	Progressed at date of lost to follow-up

Analogous to other efficacy endpoints, an exploratory analysis will be performed on PFS incorporating additional response assessments where subjects are treated with pembrolizumab following initial progression; details on this analysis will appear in the sSAP.

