7.1.1.5.4 Subsequent Antineoplastic Therapy

The investigator or qualified designee will review all new antineoplastic therapy initiated after the last dose of trial treatment. If a subject initiates a new antineoplastic therapy within 30 days after the last dose of trial treatment, the 30 day Safety Follow-up visit must occur before the first dose of the new therapy. Once new antineoplastic therapy has been initiated the subject will move into survival follow-up.

Collect transplant parameters after study treatment to include the conditioning regimen, date, and type of transplant.

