7.1.2.7.4 Disease Response Assessments/Imaging During the Trial

Following screening, disease response assessments will occur at Week 12 (± 7 days) and every 12 weeks (± 7 days) as detailed in the Trial Flow Chart in Section 6.0. The first

assessment may be performed earlier than 12 weeks if, in the opinion of the investigator, the subject is clinically progressing.

Imaging assessments should be performed (every 12 weeks from the first dose of study medication). There is a ± 7 day window for assessments performed after entry in the study. If PET and CT scan at Screening are negative for disease involvement in the neck, subsequent CT scans may not include neck. If PET or CT scans at Screening are positive for disease involvement of the neck, subsequent CT scans must include neck. Following screening, CT scans should be repeated every 12 weeks for subsequent assessments. PET should be repeated at Week 12, Week 24, or to confirm CR and as clinically indicated. PET to confirm PD is strongly encouraged, but not required, if CT clearly demonstrates PD. Disease assessments and imaging should not be delayed for delays in cycle starts.

Disease assessments and imaging should continue to be performed until documented disease progression by investigator assessment, the start of new anti-cancer treatment, withdrawal of consent, death, or the end of the study, whichever occurs first.

During Second Course, imaging should continue to occur every 12 weeks (+/- 7 days) following the same parameters listed above.

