8.4.1 Efficacy Endpoints

Efficacy endpoints that will be evaluated are listed below, followed by the descriptions of the derivations of selected endpoints.

The primary efficacy endpoint is the ORR for each cohort, defined as the proportion of subjects in the analysis population who have CR or PR at any time during the study, prior to disease progression. For rrPMBCL, response assessment will be based on IWG criteria (Cheson, 2007 [1]) using independent central review. For subjects with rrRS, IWG criteria with special considerations for RS will be used (Section 12.7). A secondary efficacy endpoint is ORR based on investigator assessment.

Other secondary efficacy endpoints include: (1) PFS, defined as the time from first dose of pembrolizumab to the first documented disease progression or death due to any cause, whichever occurs first; (2) DOR, defined as time from first response (CR, PR) to disease progression in subjects who achieve a PR or better, (3) DCR, defined as the proportion of subjects in the analysis population who have CR, PR, or SD at any time during the study prior to disease progression and (4) OS, defined as time from first dose to date of death.

PFS, DOR, and DCR will be based both on central review (primary) and investigator assessment (secondary).

Exploratory efficacy endpoints include ORR, PFS, DOR, and DCR, incorporating response assessments for subjects continuing pembrolizumab treatment after initial progression. An additional exploratory endpoint is the ORR based on the Lugano classification [2] using independent central review.

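### Table 9 censors PFS at new anticancer therapy only for subjects who do not later progress or die, so censoring depends on later outcome; separately, DOR is defined in two ways

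*Combined protocol and SAP*

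**What the plan says.** Section 8.4.1 defines PFS as "time from first dose of pembrolizumab to the first documented disease progression or death due to any cause, whichever occurs first". New anticancer therapy is not mentioned.

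In the primary column of Table 9 (8.6.1.3), subjects with no PD and no death who start new treatment are "Censored at last disease assessment before new anticancer treatment". The two rows for PD or death, split by number of missed assessments, both read "Progressed at date of documented PD or death" in that column, with no condition on new treatment. The text adds: "Death is always considered as a confirmed PD event".

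Sensitivity Analysis 1 keeps the same new-therapy row. It changes only PD or death after two or more missed assessments, which it censors at the last assessment before the gap. Sensitivity Analysis 2 is described as applying "for subjects without documented PD or death", and its table entry for those who start new therapy is "Progressed at date of new anticancer treatment". The text dates that event at the later of stopping treatment and starting new treatment; the table names new treatment only.

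Follow-up differs after new therapy. Imaging runs "until documented disease progression by investigator assessment, the start of new anti-cancer treatment, withdrawal of consent, death, or the end of the study" (7.1.2.7.4), whereas section 7.1.1.5.4 says: "Once new antineoplastic therapy has been initiated the subject will move into survival follow-up".

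For DOR, 8.4.1 ends the response at disease progression. Section 8.6.1.4 ends it at progression or death from any cause. It censors responders without progression who receive other antitumor treatment, but does not say what happens if they then die.

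**The concern.** Kaplan-Meier needs censoring that does not depend on what happens afterwards. Table 9, read row by row, sorts subjects who start new therapy by whether they later die. The resulting curve estimates neither PD or death with censoring at new therapy, nor PD or death regardless of new therapy.

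The rrPMBCL cohort is re-analysed at about 9 and 12 months, at 2 years and then yearly (text after Table 10). A subject censored in one update can re-enter the risk set in the next because of a death, so the early part of the curve can move with no new early data. Two programmers could also build different datasets from the same table.

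For DOR, the 8.4.1 wording lets a response continue through a death without PD, which lengthens it.

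**Working it through.** The plan gives no PFS or DOR event count, median or rate, so there is no figure to reproduce. The check is a reading of the rules, followed by illustrations under stated assumptions.

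**1. Two subjects with the same history.** Both have a last scan without PD at Week 24 and start new therapy at Week 26. One dies at Week 60; the other is alive at the cut-off. Under the primary column the first is at risk to Week 60 with an event, and the second is censored at Week 24. With a cut-off before Week 60, both are censored at Week 24. Later events of this kind are in practice deaths, because imaging stops at new therapy and survival contact continues (7.1.5.4.2).

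**2. Hand case (hypothetical).** Twenty subjects are at risk at month 6; 4 start new therapy without PD; 1 of these dies at month 9; nothing else happens. The Kaplan-Meier factor is 1 - d/n.
- Table 9: 3 survivors censored, n = 17, 1 - 1/17 = 16/17 = 94.1%.
- Censor all 4: n = 16, no event, 16/16 = 100%.
- Keep all 4 at risk: 1 - 1/20 = 95.0%.

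**3. Size under assumed rates.** Inputs, none from the documents:
- Exponential time to PD, with median 3, 6 or 12 months.
- 10% or 30% of those progression-free at month 6 start new therapy, with the last scan 0.5 month earlier.
- 12-month probability of death after new therapy of 10%, 25% or 50%.
- No PD seen after new therapy; cut-off at 24 months.

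This gives 3 x 2 x 3 = 18 cells. Three of them, as S(12)/S(24) in %, with simulation error of about 0.2 points:

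| Median, % starting, 12-month death | Table 9 | Censor all | Keep all at risk |
|---|---|---|---|
| 6, 10%, 25% | 25.1/6.0 | 24.9/6.2 | 26.9/8.9 |
| 6, 30%, 25% | 25.4/5.4 | 24.4/6.2 | 30.5/14.1 |
| 12, 30%, 50% | 47.3/19.5 | 49.3/24.7 | 50.1/25.0 |

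Over all cells, Table 9 minus censor-all is -2.1 to +1.8 points at 12 months and -5.2 to 0 at 24 months. With 10% starting new therapy it is -0.7 to +0.5 and -1.6 to 0. A second set of assumptions (median 6 or 9 months, 10% to 30% switching at random times, median survival after the switch 9 or 18 months) gives -1.1 to +2.6 and -3.9 to -0.1.

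The sign at 12 months is not fixed because two effects oppose each other. Those who will die add event-free time after their last scan, which raises the curve. Their deaths are then counted against a risk set from which the survivors have been removed, which lowers it. For scale, the standard error near 25% with n = 50 is sqrt(0.25 x 0.75/50) = 0.061, about 6 points.

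**4. Sensitivity analyses.** The plan does not say whether scans not done after new therapy count as missed. If they do, Analysis 1 censors deaths after about month 11 (5.5 months plus two 12-week intervals) but still counts earlier ones. In the cell median 12, 30%, 50%, S(12) is then 44.7 against 49.3 for censor-all, while the 24-month gap narrows from -5.2 to -2.3 points. Analysis 2 dates the event at new therapy for survivors but at death for those who die. Its S(12) exceeds the version with every new-therapy start as an event by 0.3 to 7.5 points (for example 42.6 against 35.1 at median 12, 30%, 50%).

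**5. Drift between updates.** Assume uniform accrual over 12 months, median 6, 30%, 25%. The primary 12-month estimate at cut-offs 9, 12, 24 and 36 months after the last subject is 24.0, 24.5, 26.3 and 27.5, against a constant 24.5 for censor-all. With 10% it is 24.8, 24.9, 25.4 and 25.8.

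**6. DOR.** Suppose responders have 6 PD events and 2 deaths without PD (assumed). Section 8.4.1 counts 6 events and 8.6.1.4 counts 8. Under a constant hazard the 8.4.1 median is 8/6 = 1.33 times as long.

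**The case against.** The best reply is that the new-therapy row describes status when new therapy starts, so that everyone who switches is censored alike, and that the sentence on death only means that a death needs no confirmation. That reading is possible and may be what was intended. The table does not say it, however. It conflicts with the unconditional wording on death, with the 8.4.1 definition, and with Analysis 2 being limited to subjects without PD or death. The text needs an edit under either reading.

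A second reply is that Sensitivity Analysis 1 already deals with late deaths. This stands in part. If unperformed scans count as missed, Analysis 1 removes the drift between the 12- and 36-month cut-offs in the assumed model and narrows the 24-month gap. It still counts early deaths, so its handling still depends on outcome, and its 12-month estimate can lie further from censor-all than the primary one does.

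Third, censoring all switchers is not the only coherent rule. This stands. It narrows the death-from-any-cause definition in 8.4.1, and keeping every such subject at risk is also consistent. A reader might infer that the plan is wrong not to censor everyone; the documents support only the need for one rule.

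Fourth, 8.6.1.4 is the operative section for DOR and includes death, so an analyst would probably count it. That makes the mismatch a wording error, but 8.4.1 names death for PFS and omits it for DOR in the same sentence.

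**Conclusion.** The point holds as a defect of wording with statistical consequences. As written, primary PFS censoring at new therapy depends on later outcome, neither sensitivity analysis applies one rule to all such subjects, and DOR has two definitions. Severity is minor to moderate.

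The size is unknown, because the documents do not say how many subjects start new therapy without PD and then die. Under the assumptions shown, the gap to censor-all is about -2 to +2 points at 12 months and -5 to 0 at 24 months. It stays within about 1 and 2 points if 10% switch, which is small beside a standard error of about 6.

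A reader might infer that reported PFS is biased in a known direction, or that the efficacy conclusion is unsafe. The documents support neither. The direction at 12 months varies with the assumptions, PFS and DOR are descriptive secondary endpoints, and the ORR test, alpha and power are untouched.

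**What to change.** 1. **Primary PFS.** State one new-therapy rule that does not look at later outcome. Since imaging stops at new therapy, the simplest is to censor every subject who starts it before documented PD or death at the last prior assessment, and to align the sentence on death in 8.6.1.3 and the PFS definition in 8.4.1. If the sponsor prefers to count death from any cause regardless of new therapy, keep all such subjects at risk and state that PD is unobserved after new therapy, so late PFS may be overstated. Report the rule not chosen as a sensitivity analysis.
2. **Planned sensitivity analyses.** Use the chosen rule in Analysis 1, and say whether scans not done after new therapy count as missed. In Analysis 2, date the event by one rule for all such subjects, including those who later die, and reconcile the table with the text on the later of stopping treatment and starting new treatment.
3. **DOR.** Define it in 8.4.1 as time to PD or death from any cause, as in 8.6.1.4, and apply the same new-therapy rule there.

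The cost is edits to 8.4.1, 8.6.1.3, Table 9 and 8.6.1.4, plus a decision on which PFS quantity is wanted. No new data are needed and the sample size does not change. Each rule has a price. Censoring at new therapy drops later deaths and may be informative. Keeping everyone at risk exceeds censor-all by 0.2 to 7.3 points at 12 months and 0.1 to 11.1 at 24 months in the assumed grid, because later PD is not seen.

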8.6.1.4 Duration of Response

DOR is defined, only for the subgroup of subjects who achieve CR or PR, as the time from start of the first documentation of objective tumor response (CR or PR) to the first documentation of tumor progression or to death due to any cause, whichever comes first. The analysis will consist of Kaplan-Meier estimates. Duration of response data will be censored on the date of the last disease assessment documenting absence of PD for subjects who do not have tumor progression and are still on study at the time of an analysis, are given antitumor treatment other than the study treatment, or are removed from study prior to documentation of tumor progression.

An exploratory analysis will be performed including response duration for those subjects who continue to receive pembrolizumab following progression and later achieve CR or PR.

8.6.1.5 Overall Survival

The median OS, if reached, will be estimated in the given analysis population. In addition, the Kaplan-Meier method will be used to estimate the survival curve.

Table 10 Efficacy Analysis Methods for Primary and Secondary Efficacy Endpoints

Endpoint/Variable	Statistical Method	Analysis Population	Missing Data Approach
Primary:			
Objective Response Rate (ORR) 
 Central review 	rrPMBCL: Exact test of binomial parameter; Point Estimate and 2-sided 95% exact CI rrRS: Point estimate and 2-sided 90% exact CI	ASaT/FAS	Subjects with missing data are considered non-responders
Secondary:			
Objective Response Rate (ORR) 
 Investigator Assessment 	Point estimate; 2-sided 90% exact CI	ASaT/FAS	Subjects with missing data are considered non-responders
Progression-free survival (PFS) 
 Central review Investigator assessment 	Summary statistics using Kaplan-Meier method	ASaT/FAS	Censored at last assessment (see Table 9 for sensitivity analyses based on alternative censoring)
Duration of Response (DOR) 
 Central review Investigator assessment 	Summary statistics using Kaplan-Meier method	All responders	Non-responders are excluded in analysis
Disease Control Rate (DCR) 
 Central review Investigator assessment 	Point Estimate; 2-sided 90% exact CI	ASaT/FAS	Subjects with missing data are considered non-responders
Overall survival (OS)	Summary statistics using Kaplan-Meier method	ASaT/FAS	Censored at last assessment
Abbreviations: ASaT – All Subjects as Treated; CI – confidence interval; FAS – Full Analysis Set; rrPMBCL – relapsed or refractory primary mediastinal B-cell lymphoma; rrRS – relapsed or refractory Richter Syndrome;			

For the rrPMBCL cohort, efficacy updates for the parameters in the above table will be conducted using a data cut-off based on when the last subject remaining on study has completed approximately 9 months and 12 months of efficacy assessments and then at 2 years after the last subject initiated treatment, which corresponds to the end of the protocol-specified treatment period. No formal statistical testing is planned. Subsequent yearly analyses will be conducted (i.e., 3 years after the last subject initiated treatment, etc.) until the trial is complete, including follow-up information on subjects who enter the re-treatment period.

8.6.2 Statistical Methods for Safety Analyses

Safety and tolerability will be assessed by clinical review of all relevant parameters including AEs, ECIs, laboratory tests, vital signs, and ECG measurements.

Summary statistics (counts, percentage, mean, standard deviation, etc.) will be provided for the safety endpoints as appropriate.

8.6.3 Summaries of Baseline Characteristics, Demographics, and Other Analyses

8.6.3.1 Baseline Characteristics and Demographics

Baseline characteristics will be assessed by the use of tables and/or graphs. No statistical hypothesis tests will be performed on these characteristics. The number and percentage of subjects screened, allocated, the primary reasons for screening failure, and the primary reason for discontinuation will be displayed. Demographic variables (e.g., age, gender), baseline characteristics, primary and secondary diagnoses, and prior and concomitant therapies will be summarized by descriptive statistics or categorical tables.

8.6.3.2 Other Analyses

Descriptive statistics, including cross-tabulations, will be performed for those subjects with evaluable samples, to assess PD-L1 expression using immunohistochemistry will be analyzed in the context of response (CR, PR, SD, PD).

Additional exploratory analyses will be described in the sSAP.

8.7 Interim Analysis

rrPMBCL:

An interim analysis will be conducted after all subjects (approximately 50) have enrolled into the rrPMBCL cohort and will consist of between 50% to 60% of the treated population who are evaluable for response, i.e., up to and including that subject at the cut-off who have reached the Week 12 assessment or have discontinued study therapy prior to Week 12. The selection of at least half of the treated population as the minimum is intended to minimize statistical bias and corresponds to a rejection boundary greater than twice that of the historical control (15%), which would be clinically meaningful. The actual boundaries used for the interim and final analyses will be based on the actual number of response evaluable subjects in the interim analysis as well as the total known treated subjects using the corresponding alpha-spending function.

[Table 11](#) below summarizes the timing and decision guidance for the interim and final analysis for ORR.

Table 11 Decision Guidance at Each Efficacy rrPMBCL Analysis

Analysis	Criteria for Conduct of Analysis	Value	Efficacy §
Interim ORR	50-60% of treated subjects are evaluable* for response	P-value** at bound ORR at bound Number of responders	0.0029 36.7% 11
Final ORR	All treated subjects are evaluable* for response	P-value** at bound ORR at bound Number of responders	0.0132 28.0% 14

Abbreviations: ORR – objective response rate; rrPMBCL – relapsed or refractory primary mediastinal B-cell lymphoma.
 Note: O’Brien-Fleming Type I error spending function used to construct boundaries (see Section 8.9)
 § Assumes 30 response evaluable subjects in interim analysis and a total of 50 treated subjects in rrPMBCL
 * Treated subjects who have reached Week 12 assessment or have discontinued study therapy prior to Week 12
 ** One-sided

There is no planned stopping early for futility or superiority; the study will continue to enroll the rrPMBCL cohort completely.

